### 9.7.7 Crude and Adjusted Measures of Association: Cohort Design

The analyses described below will address primary objective 4 and exploratory objectives 2.

- The analysis will compare subjects vaccinated with AZD1222 with the concurrent unvaccinated comparators and historical comparators to estimate the effect of receiving any dose (a first or a second), under the assumption that the effect of either dose is homogeneous. The effect of each individual dose on AESIs, will be estimated as prior vaccine exposure may “prime” the immune system.
- For outcomes that have **known risk windows**, we propose to estimate crude and adjusted IRRs and IR differences with 95% CIs using Poisson regression models. Specifically, the IRRs would be estimated using Poisson regression with robust estimation of the variance to account for individuals who may contribute person-time at different points to the exposed and unexposed cohorts (Zou 2004). For anaphylaxis and sudden death, crude and adjusted PPRs and PPDs with 95% CIs will be estimated using Poisson regression models with robust estimation of the variance to account for individuals who may contribute person-time to the exposed and unexposed cohorts at different timepoints.
- For outcomes **with unknown risk windows**, we propose estimating crude and adjusted relative risks and absolute risk differences. The relative risk (HRs) and 95% CI will be estimated using Cox regression models with robust estimation of the variance time-to-event analyses (Allison 2010). Using Cox regression models allows the flexibility to potentially adjust for time-dependant covariates, such as intercurrent COVID-19 infection.
- Adjustment for confounding will occur using PS, either through PS matching or by analytic methods involving stratification or weighting, which will be specified in the SAP. In the event that important covariates remain imbalanced after final selection of the cohorts for comparative analyses, additional approaches for confounding adjustment will be considered, including double-robust methods (ie, including the covariate in the outcome model as a separate term) or through analyses that restrict the population to subjects with more similar baseline characteristics (eg, subjects without substantial comorbidity).

The analysis described below will address exploratory objective 3

- The analysis will compare subjects vaccinated with 2 doses of AZD1222 with the active comparator cohort consisting of those vaccinated with 2 doses of an mRNA vaccine.
- For outcomes that have **known risk windows**, we propose to estimate crude and adjusted IRRs and IR differences with 95% CIs using Poisson regression models. For anaphylaxis and sudden death, crude and adjusted PPRs and PPDs with 95% CIs will be estimated using Poisson regression models.
- For outcomes **with unknown risk windows**, we propose estimating crude and adjusted relative risks and absolute risk differences. The relative risk (HRs) and 95% CI will be estimated using Cox regression models with robust estimation of the variance time-to-event analyses ([Allison 2010](#)). Using Cox regression models allows the flexibility to potentially adjust for time-dependant covariates, such as intercurrent COVID-19 infection.
- Adjustment for confounding will occur using PS, either through PS matching or by analytic methods involving stratification or weighting, which will be specified in the SAP. In the event that important covariates remain imbalanced after final selection of the cohorts for comparative analyses, additional approaches for confounding adjustment will be considered, including double-robust methods (ie, including the covariate in the outcome model as a separate term) or through analyses that restrict the population to subjects with more similar baseline characteristics (eg, subjects without substantial comorbidity).

### 9.7.8 Crude and Adjusted Measures of Association: SCRI Design

The analyses described below will address primary objective 4.

For comparative analysis using the SCRI approach, conditional Poisson regression will be used to estimate IRRs and 95% CIs. The primary SCRI analysis will include all qualifying events following dose 1 or dose 2 of AZD1222 (Sections [9.2.1.3](#) and [9.2.3.2](#)). Exploratory analyses may stratify by dose. Time-invariant confounders will be inherently adjusted for using the SCRI design, however, time-varying confounders may be included as covariates in regression models. Definition of any time-varying confounders and analytic approach will be specified in the SAP.

### 9.7.9 Subgroup Analyses

Subgroup analyses of special populations of interest (Section [9.2.1.2](#)) will be conducted using the analogous approaches used for the general study population described in Sections [9.7.1](#) (*Secondary Objective 1*), [9.7.2](#) (*Secondary Objective 2*), [9.7.6](#) (*Secondary Objective 3*); and [9.7.7](#) and [9.7.8](#) (*Secondary Objective 4*). No dose-specific analyses are planned for subgroups, given the expected limited precision of estimates.

Subgroup analyses may also be conducted based on age groupings.

No quantitative evaluations of effect modification are planned, however, for each AESI, forest plots will be generated for each subgroup and for the general population to facilitate visual comparison.

### 9.7.10 Sensitivity Analyses

For each of the matched cohort populations (ie, AZD1222 cohort with concurrent unvaccinated comparator cohort, AZD1222 cohort with active comparator cohort, and AZD1222 cohort with historical comparator cohort), the following sensitivity analyses will be conducted analogously to the main analysis:

- The direct effect of vaccination with AZD1222 on the AESIs will be estimated, excluding subjects with prior COVID-19 diagnosis and thus censoring their follow-up at the occurrence of a COVID-19 diagnosis.
- The effect of partial censoring within matched pairs on the AESIs will be estimated by censoring both members of a matched pair when one member is censored.
- For thrombocytopaenia with bleeding, an alternative risk window of 1 to 28 days at the index date (instead of the 1 to 42 days in the primary analysis) will be assessed.
- For TTS; 3 alternative risk windows of 1 to 14 days, 1 to 21 days, and 1 to 28 days after the index date (instead of 1 to 42 days in the primary analysis) will be assessed.
- For TTS; an alternative definition of the outcome will include not only thrombocytopaenia with venous thromboembolisms but also thrombocytopaenia with AMI or stroke. The risk window between thrombocytopaenia and AMI or stroke will be the same as the one used for venous thromboembolism, ie, 10 days.
- For TTS; AESI cases will be restricted to confirmed cases (ie, excluding cases that could not be validated). The resulting positive predictive values (PPVs) will be used to correct the observed PPV from the main results. This analysis will be performed depending on the total number of outcomes that will be validated (as detailed in Section 9.3.2.1.1).
- In CPRD, a sensitivity analysis using hospital data to assess the AESIs will be performed at the time of the final analysis. However, depending on the duration of the lag time for hospital data at the time of the final analysis, the analysis using hospital data may be considered as the primary analysis.

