**Table 1 Amendments, Updates, and Adjustments**

Version number	Date	Section of study protocol	Amendment or update	Reason
4.0	10 Oct 2022	9.7.10	New sensitivity analysis: Analysis to estimate the effect of partial censoring within matched pairs on the AESIs will be estimated by censoring both members of a matched pair when one member is censored (to be applied in analyses for final report)	To assess potential informative censoring
4.0	10 Oct 2022	6	Final report to be submitted in June 2024	Based on PRAC communication 10 Aug 2022. To be able to conduct all the additional activities requested with additional comparator cohorts
4.0	10 Oct 2022	5	Analyses for Interim Report 3 will not be conducted, so Interim Report 3 will not be produced	Based on PRAC communication 10 Aug 2022. The last period of administration of AZD1222 vaccines was covered in Interim Report 2. The MAH proposes to conduct only the final analyses including the maximum length of follow-up which (see row above) require considerable additional resources and time
4.0	10 Oct 2022	5	Progress Report 2	Based on PRAC communication 10 Aug 2022. To provide status update in the absence of Interim Report 3
4.0	10 Oct 2022	5	Feasibility assessment report for comparative analysis	To assess the comparability between the AZD1222 and the active comparator cohorts
4.0	10 Oct 2022	Throughout document, especially 9.4.1 and 9.6	Edits to align language with SAP V1.0 and Interim Reports 1 & 2	To achieve alignment of terminology used across the study documents
3.0	07 Jul 2021		Submitted to EMA. Endorsed by EMA	Modified in response to PRAC review

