### 9.1.1 Retrospective Cohort Design

A retrospective cohort of exposed subjects will be selected. Subjects will enter the exposed cohort upon their first vaccination with AZD1222. Subjects in the AZD1222 cohort will be matched, as applicable, to 3 different comparator cohorts: concurrent unvaccinated subjects, active comparators (ie, subjects vaccinated with an mRNA vaccine against COVID-19), and historical comparators enrolled in the study data sources during the pre-pandemic period (ie, from 2017 to 2018). The AZD1222 cohort will be matched, as applicable, independently to the 3 different comparator cohorts on calendar date of vaccination, age, sex, region, prior COVID-19, and status according to each of the 5 special populations (Section 9.2.1.2). Propensity scores (PSs) will be used to address confounding, balancing multiple covariates such as comorbidities, markers of healthcare utilisation and comedication between the vaccinated and the different comparator cohorts (Austin 2014, Webster-Clark et al 2021). Relative risk will be the main measure of effect, which will be estimated using incidence rate ratios (IRRs), prevalence proportion ratios (PPRs), or hazard ratios (HRs), depending on the analysis and outcome. Absolute risk difference measures will include incidence rate differences, prevalence proportion differences (PPD), and  $1 - KM^2$  differences.

In the cohort study, the initial plan was to use concurrent, rather than historical, comparator (unvaccinated) subjects because they are at risk for COVID-19, and COVID-19 may function as an important covariable in the analyses of several of the safety endpoints. Moreover, both healthcare-seeking behaviours and healthcare delivery during the pandemic differ from those during the pre-pandemic era. The potential challenge with this approach is that during the pandemic, concurrent unvaccinated subjects in the comparator group may themselves become vaccinated over time. Results from Interim Reports 1 and 2 confirmed that the duration of follow-up among concurrent unvaccinated subjects was short (median, < 2 months in all data sources) and probably not long enough to evaluate AESIs with unknown risk window—(those with a risk window that ends at 180 or 365 days). Thus, additional comparators for whom the follow-up is expected to be longer were requested by the PRAC and have been added to the

---

[figure not shown]
 KM, Kaplan-Meier estimate.

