**Figure 4. Time at Risk for an AESI With a Known Risk Window in Subjects With 2 Doses of AZD1222**

AESI, adverse event of special interest.

- For the evaluation of AESIs with an **unknown risk window** (those with a risk window that ends at 180 or 365 days), follow-up will comprise all person-time after the index date and will extend 180 or 365 days (Table 3) after the last AZD1222 or mRNA vaccine dose (dose 1 if only 1 dose was received and dose 2 if 2 or more doses were received) for vaccinated subjects or the corresponding time for the unvaccinated and historical comparators.
- For the AZD1222 cohort:
  - 365 days after the second vaccine dose. This rationale is 2-fold. First, because we expect that most comparators will become vaccinated during the study period, this choice will reduce the anticipated mismatch of follow-up time duration between the exposed and comparator cohorts. Second, although the risk window for some AESIs is not defined, vaccine-associated adverse events are unlikely to manifest beyond 1 year. To include person-time in the risk window when a vaccine effect could not reasonably occur may attenuate risk estimates, if a true risk exists.
  - The date on which the subject received a dose of any COVID-19 vaccine other than AZD1222.
  - The date on which a subject receives a 3rd dose of any COVID-19 vaccine
- For the active comparator cohort:
  - 365 days after the second vaccine dose.
  - The date on which the subject received a dose of any COVID-19 vaccine other than Comirnaty or Spikevax.
  - The date on which a subject receives a 3rd dose of any COVID-19 vaccine
- For the concurrent unvaccinated cohort, the date on which the subject received a dose of AZD1222, at which time the subject switches from the comparator to the AZD1222 cohort.

- For the historical comparator cohort, 31 October 2019, an estimate of the date when SARS-CoV-2 started to circulate in Europe.

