**Figure 6 Summary of Covariate Ascertainment in Cohort Analyses**

a Earliest end date of study period, enrolment termination date, death, vaccination with any COVID-19 vaccine other than the vaccine granting access to the cohort, also for each specific AESI: date of the AESI, end of risk window for that specific AESI.

Note that information on inclusion, exclusion, and covariate assessment windows will all be available before the index date in each data source, except when an alternative look-back-specific risk window is specified. For comedications and healthcare utilisation, this time window will be 183 days before the index date, except if a different time window is specified for specific medications or healthcare utilisation measures.

AESI, adverse event of special interest; COVID-19, coronavirus disease 2019.

Source: Original design diagram template can be found at [www.repeatinitiative.org/projects.html](http://www.repeatinitiative.org/projects.html).

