For AESIs evaluated using SCRI, it is assumed that the occurrence of the event must not censor or affect the observation period, however, if such events are frequently fatal, this may relevantly impact the evaluation. To assess whether this outcome occurs, we will evaluate and report the number of fatal AESI that led to a censoring of the risk interval.

This study plans to estimate the risk of AESIs among subjects who have been vaccinated compared with unvaccinated with similar health conditions. Subjects who do not receive vaccination (or receive it later) may have different health status and patterns of healthcare compared with those who are vaccinated. These differences may include a higher prevalence of frailty or underlying chronic conditions ([Webster-Clark et al 2021](#)) among vaccinees. In studies involving vaccines, special attention should be given to bias related to **healthy vaccinee bias** and **confounding by indication** ([Remschmidt et al 2015](#)). While healthy vaccinee bias refers to the situation in which subjects who have better health conditions are more likely to be vaccinated; thus, confounding by indication may be present if subjects with underlying chronic diseases are more likely to be vaccinated than healthy study subjects. Although both situations could occur in this study, it is more likely that vaccination, at least at the beginning of the study period, will be preferentially directed to subjects with more underlying conditions. To address these potential bias/confounding issues, the current study is designed to first match subjects in the vaccinated cohort with comparators of the same age, sex, and at the same calendar date, and then use PS to adjust for potential confounders, including patterns of prior healthcare use.

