It is expected that the subject groups targeted for vaccination will change over the course of the study in all countries. Matching on calendar date and age will address this concern and may also reduce potential confounding due to changing patterns of SARS-CoV-2 infection (including the potential for herd immunity to develop over time) and for changes in healthcare-seeking behaviours that have been observed during the pandemic. Being unvaccinated may also be related to lifestyle choices that are difficult to measure. It is unlikely that the data sources will have information on all potential confounders. Failure to account for variables that are unmeasured (or imperfectly measured) may lead to **residual confounding** ([Webster-Clark et al 2021](#)). To address potential confounding, the SCRI, which automatically adjusts for time-invariant confounders, will be used as a secondary approach, and using only postvaccination control periods will avoid the potential bias that use of prevaccination control periods may introduce, as prevaccination health events may affect the probability of exposure.

However, the SCRI design is not well suited to study outcomes with gradual onset, long latency, or risk periods that are not well known.

It is conceivable that over the study period, as more of the population has received vaccines to prevent COVID-19, the population of potential **concurrent unvaccinated comparators will dwindle** or that people who remain unvaccinated may be systematically different from those who choose to be vaccinated. Additionally, the age restrictions on the use of AZD1222 imposed in the UK, Spain, Italy, or the Netherlands, as in most European countries, may make it difficult to find comparable controls for the cohort study. If such a scenario develops, it is proposed to use the SCRI analysis, which includes only exposed individuals, to evaluate vaccine-AESI associations for outcomes that are suitable for this design (Table 3). In the first year of the current study, the availability of comparators and the duration of their follow-up time have been monitored. The results from analyses for the first and second interim reports confirm that the number of concurrent unvaccinated comparators was appropriate; however, the duration of follow-up was too short to evaluate outcomes with long risk windows. For this reason, the protocol was amended to include an active comparator cohort and a historical comparator cohort.

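### Pair-censoring can reveal informative censoring of unvaccinated comparators only through factors matched within pairs; for unmatched factors its agreement with the main result proves nothing

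*Protocol*

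**What the plan says.** Protocol section 9.2.3.1 ends comparator follow-up at vaccination: "For the concurrent unvaccinated cohort, the date on which the subject received a dose of AZD1222". The footnote to Figure 6 is wider and lists "vaccination with any COVID-19 vaccine other than the vaccine granting access to the cohort". Either way, exit from the comparator cohort is driven by vaccination.

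This censoring is heavy. Section 9.1.1 reports that "the duration of follow-up among concurrent unvaccinated subjects was short (median, < 2 months in all data sources", and section 9.5 expects a 3:1 ratio of vaccinated to unvaccinated person-time although matching is now 1:1.

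The protocol also says that the censoring is related to health. Section 9.9.1 states: "Subjects who do not receive vaccination (or receive it later) may have different health status and patterns of healthcare". It adds that "people who remain unvaccinated may be systematically different from those who choose to be vaccinated".

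Concurrent comparators are matched on index date, age (within 2 years), sex, prior COVID-19 and status on the five special populations (section 9.2.1.1.3); section 9.1.1 adds region. The remaining covariates enter through a propensity score fixed at the index date. Section 9.7.7 then applies Poisson and Cox models.

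Section 9.7.10 lists a sensitivity analysis in which the effect of partial censoring "will be estimated by censoring both members of a matched pair when one member is censored". Table 1 gives the reason for adding it: "To assess potential informative censoring".

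**The concern.** Balance at the index date does not last if comparators with certain health characteristics are vaccinated, and so censored, sooner than others. The comparators still under observation become a selected group, and the rate ratio can move away from 1 with no vaccine effect. In a safety study, a shift below 1 can hide harm.

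The planned check stops the vaccinee when the comparator leaves. If the factor driving exit is shared within the pair, both arms lose the same kind of person and balance is kept. If it is not shared, the vaccinee is stopped at a time unrelated to the vaccinee's own health. The remaining vaccinees stay representative, while the remaining comparators are as selected as before. The two analyses then agree, and a reader told that the check assesses informative censoring would take that agreement as reassurance.

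**Working it through.** **The plan's own figure.** The documents give no figure for censoring bias. The precision calculation in section 9.5 is the one that reflects comparator censoring. For Guillain-Barré syndrome, 5 million vaccinated × 84/365.25 years × 2/100,000 = 23.0 expected events; at 3:1, comparators have 23.0/3 = 7.67. SE = √(1/23.0 + 1/7.67) = 0.417, and Φ(ln 3/0.417 − 1.96) = 0.75, as stated. If pair-censoring cuts vaccinated time to 84/3 = 28 days, events are 7.67 in each arm and the probability falls to about 0.58. The check is therefore also less precise than the main analysis.

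**Bias model (assumed inputs).** True IRR is 1. A binary factor with prevalence p is balanced at index and multiplies the event rate by R. Comparator vaccination is exponential with c = ln 2/56 = 0.01238 per day for non-carriers and k·c for carriers. The dose-2 window is days 77-118. The 56 days respects the reported median of under 2 months; p, R, k and the dose-2 timing are not in the documents.

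Comparator person-days per subject over elapsed days a to b are (e^(−ha) − e^(−hb))/h, with h = c or kc. The carrier share s of comparator time gives a relative event rate of 1 + (R − 1)s; for vaccinees it is 1 + (R − 1)p.

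Worked case: p = 0.2, R = 3, k = 0.3, dose-2 window (elapsed days 76 to 118).
- Non-carriers: (0.3904 − 0.2321)/0.01238 = 12.8 days; carriers: (0.7541 − 0.6452)/0.003713 = 29.3 days.
- s = 0.2 × 29.3/(0.2 × 29.3 + 0.8 × 12.8) = 0.364.
- Comparator rate 1 + 2 × 0.364 = 1.73; vaccinee rate 1 + 2 × 0.2 = 1.40; IRR = 1.40/1.73 = 0.81.
- Pair-censoring, factor unmatched: the carrier share among remaining vaccinees is still 0.2, so the IRR is still 0.81.
- Pair-censoring, factor matched: the vaccinee share is also 0.364, so the IRR is 1.73/1.73 = 1.00.
- Censoring weights proportional to 1/S(t given the factor) return s to 0.2, so the IRR is 1.40/1.40 = 1.00. This holds only because the factor is measured.

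Over p = 0.1-0.2 and R = 2-3, for an unmatched factor:

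| Estimate | k = 0.3-0.5 | k = 2 |
|---|---|---|
| Dose-1 window IRR | 0.99 to 0.96 | 1.02 to 1.05 |
| Pooled two-dose IRR | 0.97 to 0.91 | 1.03 to 1.09 |
| Dose-2 window IRR | 0.94 to 0.81 | 1.06 to 1.22 |
| Cox HR to day 435 | 0.92 to 0.74 | 1.05 to 1.16 |

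Pair-censoring leaves the IRR rows unchanged to two decimals. For k = 0.3-0.5 the pair-censored Cox HR is 0.94 to 0.78. That small shift comes from a different weighting of event times, not from removal of the selection.

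**Second check with other inputs.** p = 0.2, R = 3, median 50 days, k = 0.5, 365 days. Unmatched factor: 0.857 in both the main and the pair-censored analysis. Matched factor: 0.857 becomes 1.000. One factor of each kind: 0.764 becomes 0.879. A simulation of 4 million pairs agrees: 0.852 and 0.860 unmatched; 0.856 and 0.999 matched.

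**The case against.** A reader might infer that pair-censoring always reproduces the bias and detects nothing. The documents do not support that. Matching covers age, sex, prior COVID-19 and the special populations, including frailty with comorbidities, immunocompromise and autoimmune disease. Annex Table 2 places COPD, diabetes, heart failure, chronic kidney disease and dementia in the frail-with-comorbidities group. These are much of what section 9.9.1 has in mind, and for them the contrast between the two analyses is informative. The limit applies to what lies outside: smoking, healthcare use, hypertension and other cardiovascular history not in those definitions, and illness after the index date.

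Other parts of the plan help, within limits. The SCRI and the historical comparison do not depend on censoring comparators at vaccination. However, Table 3 marks some AESIs, TTS among them, as unsuitable for SCRI, and the protocol itself questions how comparable historical subjects are. Section 9.7.1 describes follow-up by matching covariates only. The negative-control window of 12 days is too short to show selection that builds over months. Section 9.7.7 mentions time-dependent covariates only as a possibility, and only for Cox models.

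The largest effects fall on long windows, for which section 9.1.1 already calls unvaccinated follow-up probably too short. The pooled two-dose bias is modest beside the random error for rare events. The operative wording in 9.7.10 speaks only of partial censoring; the informative-censoring purpose is in Table 1. The SAP is not shown and may add censoring weights or adjust for baseline factors in a way that reduces the bias. All of this stands and lowers the stakes. It does not make the check fit its stated purpose for unmatched factors.

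**Conclusion.** The point holds in a limited form. For the concurrent-unvaccinated comparison, pair-censoring can reveal selective censoring through matched factors. It cannot do so through factors not shared within pairs, so agreement with the main result is no evidence that censoring is non-informative. That pattern does not depend on the assumed values.

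The size does. With carriers vaccinated at 0.3-0.5 times the rate, the bias is about 1-4% (dose 1), 3-9% (pooled), 6-19% (dose 2) and 8-26% (Cox HR to day 435), all towards hiding harm; with carriers vaccinated twice as fast it is upward. It would be too strong to conclude that the primary estimates are biased by these amounts, or that the primary analysis must change. The documents give neither the strength of any unmatched factor nor its relation to vaccination.

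**What to change.** In section 9.7.10, for the concurrent-unvaccinated comparison, add a sensitivity analysis with stabilised inverse-probability-of-censoring weights for comparator vaccination, truncated for example at the 1st and 99th percentiles. Model vaccination on the baseline propensity-score covariates plus time-updated COVID-19 diagnosis and healthcare use, where the data source has them in time. The modelled event must be the one that censors, so section 9.2.3.1 (AZD1222 only) and the Figure 6 footnote (wider) need to be reconciled first.

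Keep pair-censoring, but state in 9.7.10 and Table 1 that it addresses unequal follow-up and selective censoring through matched factors only. Leave section 9.7.7 unchanged.

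The cost is one extra weight model per data source, weight diagnostics and somewhat wider intervals. Time-updated hospital data may arrive late: section 9.4.5 gives a 1-year lag for PHARMO databases other than general practice, and section 9.4.1 says CPRD linked data are usually updated every 6 months. The weights do not correct for unmeasured drivers of vaccination, and the report should say so.
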